2. SUMMARY OF KEY PROTOCOL INFORMATION

2.1. Changes to the Protocol Defined Statistical Analysis Plan

Changes from the originally planned statistical analysis specified in the protocol are outlined in Table 1.

Table 1 Changes to Protocol Defined Analysis Plan

Protocol	Reporting & Analysis Plan		
Statistical Analysis Plan	Statistical Analysis Plan	Rationale for Changes	
Study Completion Status	-		
Section 3.1. Study Design Study completion is defined as: IV belimumab becomes commercially available in the respective countries. Upon the decision of the sponsor to close/terminate the study.	Definition has been revised to include "the subject transferred to a different protocol".	The BEL114333 protocol intent was to include this additional criterion. Similar definition is contained within the BEL113750 OL (China only) Phase of the protocol.	
Safety			
Section 8.1.3 Safety The frequency of AEs will be tabulated by treatment groups, according to the treatment assignment during the respective DB phase of study BEL113750 or BEL112341 (C1115).	Although the adverse events in this section were initially intended to be summarised by parent study randomised treatment groups, the safety data will actually be shown as one total belimumab group.	Similar approach to other Long- Term Continuation (LTC) studies, allowing meaningful comparisons between study BEL114333 and the LTC studies.	
Section 8.1.3 Safety The number of subjects with AEs and the incidence rate of AEs will be summarised in each 6-month time interval.	Adverse events will be summarised by year interval.	For consistency with the LTC studies.	
Section 8.1.3 Safety	AE of Special Interest (AESI) will also be summarised.	AESI (serious and non-serious) of scientific and medical interest specific for GSK are being reported across the Benlysta program.	
Section 8. Data Analysis and Statistical Considerations. Immunogenicity and B cell marker data collected at the 6-month post-treatment visit will be reported separately as an addendum to the clinical study report.	Not required.	The data base will be locked once all subjects have completed their last visit of BEL114333. All data will be included in the BEL114333 CSR.	

Protocol Reporting & Analysis Plan		
Statistical Analysis Plan	Statistical Analysis Plan	Rationale for Changes
Efficacy		- tuttonalo loi onango
Section 8.1.1. Primary Efficacy Analysis and Section 8.1.2 Analysis of Additional Efficacy and Biomarkers Subjects who received subcutaneous (SC) belimumab in the BEL112341 study before joining the BEL114333 study will be evaluated separately.	Although the efficacy data for BEL112341 subjects in this section were to be analysed separately, the data will be combined with the data from subjects who received IV belimumab in the BEL113750 parent study.	There are no clinically significant differences in the results between these studies in terms of which formulation was used. Hence, the data from these 25 SC subjects can be aggregated with the subjects who received the IV formulation, unless otherwise stated.
Section 6.2.1.2 Secondary [Efficacy] Endpoints Baseline will be defined as study Day 0 of the respective studies BEL113750 or BEL112341.	For subjects randomised to placebo during the parent study BEL113750, baseline will be defined as study Day 0 of the study BEL114333. For subject randomised to placebo in the parent study BEL112341, baseline will be defined as study Day 0 of the open-label extension of BEL112341.	For consistency with the LTC studies, baseline is defined as the last available value prior to the initiation of treatment with belimumab. No additional analyses are planned as mentioned in the protocol, for placebo.
Section 6.2.1.1 Primary Endpoint The SRI response is defined as the primary efficacy endpoint.	The primary SRI response endpoint will be regarded as a key secondary endpoint for the study BEL114333.	The primary objective of the study BEL114333 is safety. Efficacy is considered as a secondary outcome.
Section 6.2.1.2 Secondary [Efficacy] Endpoints	PGA and BILAG components of the SRI response endpoint were added.	Additional analyses are being reported to enable the long-term data to be further evaluated.
Section 6.2.1.2 Secondary [Efficacy] Endpoints Number of days of daily prednisone dose ≤ 7.5 mg/day and/or reduced by 25% from baseline over time.	The threshold of a 25% reduction has been revised to 50%.	For consistency with the BEL113750 parent study definition of this endpoint. This endpoint was not considered in the parent study BEL112341.
Section 6.2.1.3 Other [Efficacy] Endpoints Duration of primary response [SRI] assessed every 24 weeks.	This endpoint has been removed.	Because the investigator has much more freedom in prescribing concomitant medications during the OL continuation study BEL114333, this could potentially confound evaluating the duration of the SRI response.
Section 6.2.1.3 Other [Efficacy] Endpoints	The following efficacy endpoints were added: Change and percent	Additional analyses are being reported to enable the long-term, data to be further

Protocol	Reporting & Analysis Plan	
Statistical Analysis Plan	Statistical Analysis Plan	Rationale for Changes
	change from baseline in SELENA SLEDAI. SLICC/ACR Damage Index Worsening from baseline.	evaluated.
Section 6.2.1.3 Other [Efficacy] Endpoints Renal flare rate and time to first renal flare assessed over time. A SLE renal flare is defined as the occurrence of 1 or more of the following criteria (not shown here) in 2 or more consecutive visits during the study. See RAP, Section 8.2.8, for details of the criteria.	The renal flare definition has been revised for study BEL114333, as the occurrence of one or more of the following criteria (not shown here) at a single visit in which assessments are performed.	Assessments every 6 months during study BEL114333 will not allow the use of the same definition of renal flares as in the respective parent studies, which requires assessments to be performed at 2 or more consecutive monthly visits.
Section 8.1 Data Analysis Considerations	Although the efficacy data will be tabulated by parent study randomised treatment groups, as mentioned in the protocol, the graphical displays will be shown for the total Safety population only.	The graphs align with the interpretation of response over time rather than comparisons between treatment groups.

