6.3.6. Time Period and Frequency of Detecting AEs and SAEs

The investigator or site staff is responsible for detecting, documenting and reporting events that meet the definition of an AE or SAE.

AEs will be collected from the start of study treatment (Week 0) and until the 16 week follow up visit.

SAEs will be collected over the same time period as stated above for AEs. However, any SAEs assessed **as related** to study participation (e.g., study treatment, protocol-mandated procedures, invasive tests, or change in existing therapy) or related to a GSK concomitant medication, will be recorded from the time a subject consents to participate in the study up to and including any follow up contact. All SAEs will be reported to GSK within 24 hours, as indicated in Section [6.3.7](#).

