8. DATA ANALYSIS AND STATISTICAL CONSIDERATIONS

There is no statistical sample size calculation. All analyses will be performed using descriptive statistics and will be exploratory in nature. The data base will be locked once all subjects have completed the Week 16 follow-up visit. Immunogenicity and B cell marker data collected at the 6-month post-treatment visit will be reported separately as an addendum to the clinical study report. Details of the analysis will be given in the Reporting and Analysis Plan (RAP).

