8.1.3. Analysis of Safety Variables

AEs will be graded for severity by the investigator using Adverse Event Severity Grading Tables ([Appendix 6](#)) or the grades in Section 6.3.4, as appropriate. The frequency of AEs will be tabulated by MedDRA system organ class and preferred term and by treatment groups, according to the treatment group that the subjects were assigned to during randomisation in the BEL113750 or C1115 study. Additional analysis may be performed based on event rates adjusting for subject-years on study agent. The number of subjects with AEs and the incidence rate of AEs will be summarised in each 6-month time interval. AEs will also be summarised by MedDRA SOCs and preferred terms for those that are considered to be at least possibly related to study agent and those that are considered to be severe (Grade 3 and Grade 4). Discontinuations due to AEs will be summarised.

The frequency of laboratory abnormalities will be tabulated by treatment group. Laboratory values will be assessed for significant changes from baseline. Laboratory toxicity will be graded using Adverse Event Severity Grading Tables when possible. Shift tables will be used to determine if subjects move from normal to abnormal during the course of the study. Shifts of ≥ 2 grades and Grade 3 or Grade 4 laboratory abnormalities will be summarised.

Immunogenicity (anti-belimumab antibodies) will be summarized at baseline and during treatment and follow-up.

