2.4.1. Treatment Comparisons

All subjects will be treated with open-label IV belimumab for the duration of the study BEL114333. The analyses will be performed on data from all subjects as one total belimumab treatment group by year of belimumab treatment.

As subjects started to receive belimumab treatment in the parent study, or the open-label extension of the parent study BEL112341, or the open-label study BEL114333, different time points to start of belimumab treatment will be used to define subject follow up in the analysis. See Figure 1.

Analyses will be based on all available follow-up from the first dose of belimumab treatment through to study end.

Additional safety (e.g., labs), efficacy and study population summaries will be presented by parent study randomised treatment groups (belimumab vs placebo); however, these comparisons will be descriptive in nature. For the remainder of the document, parent randomised treatment group will be used to refer to the treatment to which a subject was randomised in the parent study, irrespective of formulation.

Figure 1 First Belimumab Dose/Baseline Definition

Analyses will be based on all available data from the first belimumab dose through to study end, BEL114333. As subjects started to receive belimumab in the parent study, or the open-label extension of BEL112341, or the open-label study BEL114333, different timepoints to start of belimumab treatment are used in the analysis (as shown). Baseline is defined as the last available value prior to the first belimumab dose.

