7.2.1. Adverse Events

• Data from all subjects as one belimumab group will be summarised.

- All adverse event tables will show the data by year interval at the start of an AE, and include a summary over the total post-baseline period. Year interval is defined in Appendix 2: Assessment Windows.
- Any AEs that started prior to the first IP administration in the parent study will not be reported. See Section 6.2, footnote 4 in Table 4 for relevance for such AEs as past medical history terms. Only treatment-emergent adverse events will be summarised.
 - o Treatment-emergent AEs are defined as follows:
 - AEs that started on or after the first dose of belimumab treatment.
 - For those subjects who were randomised to placebo in the parent study, ongoing AEs that started before the first open-label belimumab dose (in either BEL112341 open-label extension or BEL114333) and worsened (severity, seriousness, relatedness) at any point during the open-label treatment.
 - Ongoing AEs that started before the first open-label belimumab dose which
 did not worsen during the open-label treatment (for those subjects who were
 randomised to placebo during the parent study) will not be considered
 treatment-emergent, but will be listed.
- Listings will be generated by the parent randomized treatment group (see Table 8). All treatment-emergent AEs as defined above will be listed plus any ongoing AEs that started before the first belimumab dose (for subjects randomised to placebo in the parent study) that were not considered treatment-emergent. AEs that started in each parent study will be flagged.
- The hierarchical relationship between MedDRA SOCs, PTs and verbatim text will be displayed as a listing for all AEs.
- Adverse events in BEL114333 will be coded to the current MedDRA dictionary version at the time of study reporting (version 22.0).
 - NOTE: the same version of the MedDRA dictionary which was used at the time of reporting the parent studies will be used for this current reporting (BEL113750, version 21.1; BEL112341, version 18.0). Any major coding discrepancies between different versions of MedDRA can be addressed in a CSR appendix, if necessary.

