11.2.1. Year Intervals

- To report subject disposition and AE assessments with similar durations of exposure to active belimumab treatment, assessments will be slotted into year intervals using a 365-day calendar year.
- Few subjects are expected to have > 6 years exposure and therefore "Year 6+" will be extended to the last available visit.
- For subjects who withdraw during an interval, the end date of their final interval will be set to their exit visit date.
- For summaries, the "Any Time Post-Baseline" includes the follow-up visits, where follow-up visits are excluded from the "Year 6+" year interval.
- For laboratory assessments, the worst value/highest toxicity reported over the year
 interval will be used in the analyses. Concomitant medications will be reported by
 what medications a subject is taking during the interval. In addition, AEs will be
 reported by start date. Subject disposition, worst value/highest toxicity laboratory
 assessments, concomitant medications, and AEs will be summarized according to the
 following year categories.

Study Year	Belimumal	o Study Days
	Start Day	End Day
Year 0-1	Day 1 ^[1] First Treatment Date	Day 365
Year 1-2	Day 366	Day 730
Year 2-3	Day 731	Day 1095
Year 3-4	Day 1096	Day 1460
Year 4-5	Day 1461	Day 1825
Year 5-6	Day 1826	Day 2190
Year 6+	Day 2191	Maximum Study Day [2]

NOTES:

- [1] Protocols specify Day 0 as First Treatment, but due to CDISC standard implementation first treatment date will appear as Day 1 in the analyses. Also, first treatment date refers to first belimumab treatment, regardless of originally randomized treatment.
- [2] Last visit date will be defined as the exit visit date where applicable. Subjects who do not have an exit visit date and only a follow up date, the date of the follow up will be used. See Section 11.5.1 for more details.

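### The pooled Year 0-1 AE column mixes a double-blind, completers-only first year with an open-label one, and no planned AE summary separates them

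*SAP*

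**What the plan says.** Protocol Section 8.1.3 tabulates AE frequency by treatment group, "according to the treatment group that the subjects were assigned to during randomisation in the BEL113750 or C1115 study". Protocol Section 6.3.6 fixes the collection period: "AEs will be collected from the start of study treatment (Week 0) and until the 16 week follow up visit".

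The SAP changes two things.

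- **Grouping.** Section 2.1, Table 1 records that "the safety data will actually be shown as one total belimumab group", giving comparability with the other long-term continuation studies as the reason. Section 7.2.1 repeats it: "Data from all subjects as one belimumab group will be summarised".
- **Clock.** Section 7.2.1 states: "All adverse event tables will show the data by year interval at the start of an AE". Section 11.2.1 explains that "first treatment date refers to first belimumab treatment, regardless of originally randomized treatment". Section 2.4.1 acknowledges that the starting points differ: "As subjects started to receive belimumab treatment in the parent study, or the open-label extension of the parent study BEL112341, or the open-label study BEL114333".

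Parent randomised group is kept for laboratory, immunogenicity and efficacy tables (SAP Sections 2.4.1, 7.4 and 8). For AEs it survives only in the listings, which also flag events that began in a parent study (Section 7.2.1). The AE subgroups are age, gender and baseline SELENA SLEDAI (Section 11.8.2). Neither the rationale in Table 1 nor the AE section mentions blinding status.

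**The concern.** Long-term safety is the primary objective, and its AE tables are laid out to be read across year columns. A reader will take the step from Year 0-1 to Year 1-2 as the change from early to later exposure. In these tables, that step also coincides with two changes of condition that apply unequally to the parent groups.

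- **Drug-related AEs.** Causality is the investigator's judgement (Protocol Section 6.3.4). Subjects randomised to belimumab had it made blind in the first year and open-label afterwards. Subjects randomised to placebo had it made open-label throughout their belimumab time.
- **AEs leading to discontinuation.** Subjects randomised to belimumab enter the Safety population only if they finished the parent study and then received a BEL114333 dose. Their first year is nearly free of such events by construction.

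At stake is a misread trend in the investigator-judged tables, and a misleading comparison of early with later years against the other continuation studies.

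**Working it through.** The plan has no power or precision figure to reproduce ("There is no statistical sample size calculation"). The check is on where the first year falls, and on what pooling does to each type of table.

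**Step 1. Where Year 0-1 falls**

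Inputs: Year 0-1 is study days 1 to 365, and study day = protocol day + 1 (SAP 11.2.1). The last BEL113750 double-blind dose is on Day 336 (SAP 11.1.2.1). The first BEL114333 dose follows 4 weeks later, allowed range 2 to 8 (SAP 2.3). The window around Day 336 is ignored.

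First open-label study day = 336 + gap + 1.

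| Gap (days) | First open-label study day | Year 0-1 days before it |
|---|---|---|
| 14 | 351 | 350/365 = 95.9% |
| 28 (target) | 365 | 364/365 = 99.7% |
| 56 | 393 | 365/365 = 100%, plus 392 - 365 = 27 days of Year 1-2 |

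In BEL112341 the open-label extension starts at the Week 52 visit, Day 364, so its first dose is again on study day 365. For any subject randomised to placebo, the first belimumab dose is itself open-label: 0 of 365 days are blinded.

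**Step 2. Drug-related AEs**

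Let f be the share of Year 0-1 person-time from subjects randomised to belimumab, and k the related-AE rate under open-label judgement divided by that under blinded judgement. Neither is in the documents; both are assumed. With no true change over time:

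Year 1-2 / Year 0-1 = k / (f + (1 - f)k)

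| | f = 0.50 | f = 0.67 | f = 0.75 |
|---|---|---|---|
| k = 0.8 | 0.89 | 0.86 | 0.84 |
| k = 1 | 1.00 | 1.00 | 1.00 |
| k = 1.25 | 1.11 | 1.15 | 1.18 |
| k = 1.5 | 1.20 | 1.29 | 1.33 |

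Split by parent group, the placebo column has ratio 1.00 for every k, and the belimumab column has ratio k.

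The collapsing rule in SAP 11.3.1 blurs this further. An AE recorded in both studies takes the worse of its two relatedness entries but stays in the year it began. Some Year 0-1 events can therefore carry an open-label judgement.

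**Step 3. AEs leading to discontinuation**

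Entry required completing BEL113750 through Week 48, or completing the BEL112341 (C1115) open-label extension (Protocol 4.2). The Safety population also requires a BEL114333 dose (SAP 4). The time during which a subject could hardly have had such an event is:

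| Parent study and arm | Protected until | Part of Year 0-1 protected |
|---|---|---|
| BEL113750 belimumab | study day 365 (351 to 393) | nearly all |
| BEL112341 belimumab | 364 + 168 + 1 = day 533 | all, plus 532 - 365 = 167 days of Year 1-2 |
| BEL113750 placebo | first open-label dose, day 1 | none |
| BEL112341 placebo | 168 + 1 = day 169 | 168/365 = 46% |

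The protection is not complete. AEs are placed by start date, so one that began in Year 0-1 and led to stopping after entry still counts there.

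As a rough illustration for BEL113750 subjects only, with a constant true rate d and no such late-acting events, the pooled Year 0-1 rate is f x 0 + (1 - f)d. That is 0.50d, 0.33d and 0.25d at f = 0.50, 0.67 and 0.75, against d later.

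**The case against.** The change is disclosed and has a reason. The study is descriptive, with no hypothesis test. The double-blind results were reported separately (SAP Section 1). AE listings by parent group, with a flag for events that began in a parent study, allow the split to be rebuilt. During BEL114333, sites stay blind to the earlier BEL113750 arm until those results are public (Protocol 3.2), although they know the current drug. All of this stands, and it keeps the point modest. But a listing is not a summary, and disclosing the pooling does not tell a reader that the year trend crosses unblinding.

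Four stronger readings are tempting, and the documents do not support them.

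- **That dropping the protocol's group columns created the mixture.** Protocol AE collection starts at Week 0 of BEL114333, so the protocol's own table would have covered open-label AEs in both groups. The SAP's clock brings the blinded year in; the pooling then hides it.
- **That drug-related AEs will rise artificially after Year 0-1.** The sign depends on k. At k = 0.8 the pooled rate falls, and at k = 1 nothing happens.
- **That a discontinuation step shows the effect of unblinding.** Selection on parent-study completion is the main mechanism there.
- **That group columns remove the problem.** In the parent-belimumab column the blind-to-open step remains fully confounded with time.

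**Conclusion.** The point holds in this form. Counting from first belimumab dose brings double-blind parent-study AEs into Year 0-1, and pooling leaves no planned AE summary that separates them from the open-label first year of parent-placebo subjects. The composition is well established: about 96% to 100% of Year 0-1 precedes open-label dosing for BEL113750 belimumab subjects, and 0% for placebo subjects. Later years are open-label apart from at most 27 days per BEL113750 subject at the schedule limits used here.

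The effect on drug-related AEs has unknown size and direction, because neither the arm split of the Safety population nor any related-AE rate is given. The ratios of 0.84 to 1.33 only show how the result responds to assumed values. For discontinuations, the design itself pushes the pooled Year 0-1 figure down, by an amount that depends on the unstated split.

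No analysis is invalidated. The consequence is a primary-objective trend that is open to misreading between its first two columns; comparisons among later years are little affected.

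**What to change.** Keep the total column, which fully serves the comparison with the other continuation studies. Add parent randomised group columns to the AE overview (Table 2.6) and to the drug-related and discontinuation tables: 2.10, 2.11, 2.15, 2.16, 2.20, 2.21, 2.28, 2.29, 2.35 and 2.36.

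Footnote these tables to say that:

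- Year 0-1 is double-blind and conditional on parent-study completion for parent-belimumab subjects, and open-label for parent-placebo subjects;
- BEL112341 parent-placebo subjects could have an AE leading to discontinuation only after about 6 months of open-label extension;
- only the parent-placebo column gives a year trend under one blinding condition;
- the parent-belimumab step from Year 0-1 to Year 1-2 remains confounded with unblinding.

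The cost is extra columns in eleven tables, using a grouping variable that already drives the laboratory and efficacy tables and the AE listings. The downside is longer tables and small per-group counts; only 25 subjects come from BEL112341.
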